Consent/Baseline visit, written informed consent, baseline assessments and randomization: Section 11.2 contains details of the orientation and informed consent procedures. The RA will schedule an in-person consent/baseline visit for eligible persons at the study offices at that site at which they will be given further opportunity to ask, and have answered, any remaining questions they may have about their participation. If they still wish to enroll in the trial, they will complete the written informed consent document. After providing written consent they will complete the baseline assessments. After all baseline assessments are completed, participants will be randomly assigned to one of the two study arms.

Randomization will be stratified by site and asthma severity with each stratum in randomly allocated blocks of two using the ralloc program in Stata.^{82, 83} The RA will generate the random allocation sequence, will communicate randomization status to each participant at time of randomization and the allocation table will be uploaded to the RedCap database. Participants in each cohort will be randomized altogether and sent to the same MBSR and HLC classes. This approach is necessary to ensure that the seasonality and temporal differences be balanced between the two arms. We anticipate participants will begin their intervention (MBSR or HLC) within 8 weeks of randomization. Reasons for ineligibility and for non-participation of eligible candidates will be documented through the use of a Screening Form completed by the RA. Data will be collected from all patients who provide consent to be screened but who were found to be ineligible at screening and for those found to be eligible but deciding not to participate.

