Supporting Participant Attendance at Intervention Classes: At the time of recruitment and enrollment, the RA will emphasize the importance of attending the intervention classes and ask participants if they are planning to be absent for more than one class for the upcoming cycle. If so, they will be advised to enroll in the following cycle of intervention classes. The MBSR program requires attendance at an orientation session prior to the first class, therefore the RA will call participants randomized to MBSR two days before the orientation to remind them to attend. In the two days prior to the initial MBSR and HLC classes, the RA will call all study participants to remind them that their program is starting, reiterate that they are required to attend the intervention sessions, and problem solve any challenges the participant anticipates about intervention class attendance.

To support ongoing class attendance in the MBSR arm, in addition to the call made by MBSR instructors when a person misses a class, the RA will check the MBSR attendance information for each class to check study participants' attendance for each week's classes. The RA will follow-up with a call to those study participants who have missed that class to identify barriers to participation and brainstorm strategies for attending the MBSR classes to enhance intervention adherence.

To support ongoing class attendance in the HLC arm, the HLC instructors will email the RA with the attendance list for that week's classes. The RA will follow-up with a call to those study participants who have missed that class to identify barriers to participation and brainstorm strategies for attending the HLC classes to enhance intervention adherence.

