Severity of asthma will be classified according to criteria in the tables below. The patient's medical record will be used as the criterion reference for the medications used in classification. The list of medications will be sent to both Drs. [name] (UMMS) and [name] (Miriam), the study pulmonologists, who will each make an independent determination of severity. If there is agreement between the two study pulmonologists regarding asthma severity classification, the RA will then randomize the participant according to this classification. If there is discrepancy between the two pulmonologists, the RA will provide [name] with [name] assessment and rationale and [name] will make the final asthma severity classification prior to the participant being randomized.

CLASSIFICATION OF ASTHMA SEVERITY

Step 1	Step 2	Step 3	Step 4	Step 5
No controller medication. SABA as needed (Step 1 patients are not eligible for the study)	Low-dose ICS (or other low-intensity treatment such as cromolyn, LTRA, nedocromil and theophylline)	Low-dose ICS and LABA	Med/High-dose ICS and LABA Low dose ICS+LABA+LTRA Med/High ICS/LABA +LTRA Med /high ICS/LABA +theophylline	High-dose ICS and LABA ± oral corticosteroids (and/or other extra treatment) Med/high ICS/LABA + tiotropium
Mild		Moderate	Severe	

SABA= Short-acting β_2 -agonist; ICS=inhaled corticosteroids; LABA=Long acting β_2 -agonist; LTRA=leukotriene receptor antagonists

--Steps and severity classification according to 2015 GINA guidelines (see page 21 and Box 3-5)

--Low, medium and high daily doses of inhaled corticosteroids defined per 2015 GINA guidelines (see Box 3-6)

--Alternative combinations of drugs for each step also classified per GINA 2015 guidelines

--If patient states they are on LTRA for a diagnosis other than asthma, or on oral steroids for reasons other than asthma, we will consider the medicine as an asthma therapy since it would be difficult to ascertain how they would do if that medicine was taken away.

[name] the Project Director will supervise the RAs to maintain consistent delivery of the orientation sessions, including provision of study information, obtaining informed consent, completing baseline assessments, and randomization protocol.

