9.2 Sample Size and Randomization

The trial size was determined based on hypothesized intervention effects on ACQ score, the primary outcome. We will recruit 254 individuals, but base power calculations on n=216 (108 per arm) anticipating $\leq 15\%$ loss to follow-up. With one baseline measure and 3 follow-up measures at 6, 12 and 18 months, the trial can detect an intervention effect of 0.25 ACQ score improvement using ANCOVA (or linear mixed models) method at 5% significance level and at least 80% power. This treatment effect is consistent with recent reported drug-trials for asthma control. Based on literature, for sample size estimation we assumed the mean (SD) of ACQ scores for the MBSR and HLC groups are 1.24 (0.66) and 1.49 (0.66) averaged over the three follow-up time points, respectively, and a serial correlation of 0.45 within patients. We expect to recruit patients from 12 physicians at each site, with on average each physician contributing 9 patients. Because within physician correlation has not been reported in literature and our small-sized pilot study does not allow an accurate estimation, we conservatively assumed a modest within physician correlation of 0.05. The sample size was estimated using Stata MP 12.

Our sample size estimation and power analysis are conservative and the treatment effect is chosen for other important reasons: a) to preserve the possibility of addressing treatment heterogeneity by select patient and physician characteristics (e.g. differential effects between male and female participants, ethnicity); we plan to conduct subgroup analysis and examine how treatment effects may differ. Such analysis will be very important when refining the treatment protocols and for dissemination if proved effective; b) other than the primary outcome, we are also interested in other primary/secondary outcomes described below and powered the trial to detect meaningful changes in these outcomes as well. The sample size is determined to allow us to achieve all these analytic goals, not just for the primary outcome.

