Randomization stratified by asthma severity and study site with each stratum in randomly allocated block sizes of two using the ralloc program in Stata^{82, 83} was determined most appropriate treatment assignment procedure as it will control for the majority of confounds including disease severity, location, prior conditions, race, gender etc. Procedures for the maintenance of trial randomization codes and maintaining appropriate masking for the study have been discussed in Section 6.2.3.

In total, the study will recruit 254 participants, 127 from each of the sites. The specific recruitment goals stratified by study site and asthma severity (mild, moderate or severe asthma) are: UMass Memorial Health Care (UMMHC): and the Miriam Hospital. Data is expected on 216 participants at study completion.

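### Fixed blocks of two and an unblinded enrolling RA leave some allocations foreseeable; how many depends on conflicting text about batch timing, block restart and who generates the sequence

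*Combined protocol and SAP*

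**What the plan says.** **Block size.** Section 4.3 specifies "each stratum in randomly allocated blocks of two using the ralloc program in Stata". Section 9.2 words it as "each stratum in randomly allocated block sizes of two using the ralloc program in Stata", which could suggest varying sizes, but two is the only size named there or in the Précis and Sections 3, 6.2.2 and 11.2. The strata are two sites by three severity classes.

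**Who randomizes.** Sections 4.3 and 6.2.2 say: "The RA will generate the random allocation sequence, will communicate randomization status to each participant at time of randomization". Sections 3 and 11.2 say the data manager at UMMS carries out the randomization.

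**What the RA does and knows.** Under Sections 4.3 and 6.2.2 the RA screens, obtains consent and schedules the baseline visit. The RA asks about planned absences; patients expecting more than one are told that "they will be advised to enroll in the following cycle of intervention classes". Section 6.2.2 gives the RA the agreed severity class, and so the stratum, before randomization. Section 6.2.3 leaves the RA unblinded.

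**Timing.** Sections 4.3 and 6.2.2 say: "Participants in each cohort will be randomized altogether and sent to the same MBSR and HLC classes". The Précis and Section 11.2 also describe randomization by cohort. Later in Section 6.2.2, once the two pulmonologists agree on severity, "the RA will then randomize the participant according to this classification". Section 5.2 has participants join the next available group after randomization.

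**Not stated.** The protocol does not say whether the cohort list is closed before its first member is allocated, whether blocks continue or restart between cohorts, or how the sequence is concealed from enrolling staff.

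**The concern.** A person who knows the next arm can influence whether a given patient enters, or in which cycle. This matters most when the same person screens, consents and advises on timing. The patients attend classes whose content they know, and six of the seven items of the Asthma Control Questionnaire are recalled by the patient (Section 6.2). If more motivated or more distressed patients were steered to one arm, the primary comparison could shift, and analysis as randomized would not correct it.

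Section 6.2.3 calls the effect of the unblinded RA minimal because participants complete the surveys themselves and the RA does no data entry or analysis. That answers bias in assessment and analysis. It does not address selection at entry, which is where the RA acts.

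**Working it through.** **Inputs.** 254 recruited, 127 per site, 1:1 allocation (Section 9.2); six strata; 13 cohorts (Sections 3 and 4.3); block size two. The recruitment figure reproduces: 216 / 0.85 = 254.1. The protocol gives no figure for predictability, so there is none to reproduce.

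**Assumptions.** Equal recruitment by site, patients falling at random into cohorts, and, for the formulas, three equal severity classes. The mean cell size is then m = 254 / (13 × 6) = 254 / 78 = 3.26.

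**One block.** With 1:1 blocks of two, P(second arm | first arm known) = 1. Half of all allocations in complete blocks are forced. Someone who sees past allocations guesses 0.5 + 0.5 × 0.5 = 75% correctly. Full enumeration for larger fixed blocks gives:

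| Block size | Forced | Guessed correctly |
|---|---|---|
| 2 | 50.0% | 75.0% |
| 4 | 33.3% | 70.8% |
| 6 | 25.0% | 68.3% |
| 8 | 20.0% | 66.6% |

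**Trial level: allocations known before entry, from block structure alone.**

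1. *Singly, list continuing.* Each stratum ends with half an unpaired patient on average: (254 − 6 × 0.5) / 2 = 125.5, or 49%.
2. *Singly, list restarting each cohort.* With Poisson cells, P(odd) = (1 − e^(−2m)) / 2 = 0.499. Expected pairs are 78 × (3.256 − 0.499) / 2 = 107.5, or 42%.
3. *Batch, list continuing.* Only a pair left open by an earlier cohort is exposed: 6 strata × 12 later cohorts × 0.5 × (1 − e^(−3.26)) = 34.6, or 14%. This counts one patient per open pair and presumes the RA can foresee who takes the open slot, for example by order of enrolment.
4. *Batch, list restarting.* No pair spans two cohorts, so 0.

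Simulation under three severity mixes (equal; 20/20/60; 60/20/20) gave 125.5 for case 1, 107.6 to 107.8 for case 2 and 32.6 to 34.6 for case 3. The severity mix hardly matters.

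**If the RA holds the sequence.** In cases 1 to 3 all 254 allocations are knowable in advance. The same is true of case 4 if the list and the order of filling it are fixed before enrolment. Block size is then beside the point.

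**Mixed blocks of 2 and 4**, equally likely, boundaries unmarked, mean length 3. An allocation is certain only after two like assignments open a block of four: (1/2 × 1/3 × 2) / 3 = 11%. Correct guesses are (1/2 × 1.5 + 1/2 × 2.833) / 3 = 72%. Certainty falls sharply, but guessing the under-represented arm still works nearly as well.

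**The case against.** The strongest reply is that the protocol already plans cohort-wise randomization. Four places say so, and two of them call it necessary for balance by season. The sentence about randomizing a single participant sits in a paragraph on settling severity; it names the stratum to use and sets no schedule. This stands in part. A reader might infer that the second allocation of every pair is always known in advance, or that some 107 to 125 patients are certainly exposed. The documents do not support that, because both statements need one-at-a-time allocation. The opposite inference, that batch allocation disposes of the matter, also fails: no text closes the cohort before allocation begins, and a continuing list still leaves 33 to 35 allocations open.

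Second, the room for steering is limited. Deferral depends on absences the patient reports, screening follows a script and form, reasons for non-entry are recorded, and pulmonologists set severity. These limits are real, but none of them conceals the next allocation.

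Third, small blocks serve the stated aim of balance when cells average 3.3 patients. That is a fair reason for the block size and no reason to let enrolling staff see the pattern.

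**Conclusion.** The concern holds conditionally. Known-in-advance allocations range from 0 (batch, blocks restarting), through about 33 to 35 of 254 or 13–14% (batch, list continuing), to about 107 to 125 or 42–49% (singly). All may be knowable if the RA holds the sequence. The documents do not settle which case applies, and the conflict over who generates the sequence is at least as important as the block size. The trial-level counts rest on the assumed spread of patients over cohorts and severity classes; that the second arm of a pair follows from the first does not.

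A reader might also infer that selection took place. The documents show an opportunity and no described safeguard; they give no evidence that anyone used it.

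**What to change.** 1. Reconcile Sections 4.3 and 6.2.2 with Sections 3 and 11.2, so that the data manager, and not the enrolling RA, generates and holds the sequence.
2. Reconcile the cohort-wise wording in Sections 4.3 and 6.2.2 with the single-participant step in Section 6.2.2. State that consent, baseline and severity class are complete for every cohort member before any is randomized, that the whole cohort is then allocated in one run, and that blocks restart in each cohort. Closing the cohort without restarting blocks is not enough.
3. If any patient must be randomized singly, vary block sizes at random and keep them from enrolling staff. This is a fallback: mixing 2 and 4 cuts certain allocations to about 11% but correct guesses only from 75% to about 72%.
4. If enrolment has finished, record what was actually done and report baseline Asthma Control Questionnaire scores by arm according to whether the allocation was foreseeable.

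**Cost.** Mainly wording. Restarting blocks leaves more of them incomplete: 254 − 2 × 107.5 = 39 unpaired patients are expected, so the difference in arm totals has a standard deviation of about √39 = 6.2. A split of 130 to 124 keeps (130 × 124) / 127² = 99.9% of the efficiency of equal arms. With mixed blocks on a continuing list, the largest imbalance in a stratum rises from 1 to 2 patients.

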3. THE STUDY DESIGN

The primary goal of the 5-year RCT is to evaluate the effect of MBSR on asthma symptom management as reflected in level of asthma control at 18-month follow-up. Secondary goals include examining the effects of MBSR on asthma-related QoL, perceptual accuracy of dyspnea and its mediating effect on asthma control and management, lung function, and medication use; and the cost-effectiveness of MBSR in asthma control. Two hundred and fifty four patients 18 years and older with documented mild, moderate or severe asthma^{1, 2} will be recruited from the patient population of UMass Memorial Health Care (UMMHC) and the Miriam Hospital. Data

is expected on 216 participants at study completion. Participants will be randomly assigned to Mindfulness-Based Stress Reduction (MBSR), in which they will attend the 8-week program, or a Healthy Living Course (HLC) control condition, in which they will attend an 8-week program consisting of lectures and discussion on health-related topics. Randomization will be done by the data manager at UMMS, and be stratified by site, and asthma severity with each stratum in randomly allocated blocks of two using the ralloc program in Stata.^{82, 83}

Participants will be recruited into the study in 13 cohorts over 13 quarters to coordinate with the ongoing University of Massachusetts Medical School (UMMS) and Miriam MBSR programs, and to maximize the potential pool of recruits. Assessments will be at baseline, and 6-, 12-, and 18-months post-baseline. The timeline allows sufficient time for study participant recruitment and follow-up to address the study's specific aims. See Figure 3 Study Design below. All study personnel will be blind to intervention assignment except those involved with randomization codes, delivery of the interventions, and preparation of reports for the

Figure 3. Study Design

independent monitoring. These unblinded staff will have no access to the data, no influence on the outcome assessments, and no involvement in data analysis.

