Participants will be given ample opportunity to ask questions before giving their consent and all of the potential subject's questions will be answered. While the consent process is expected to take 20-30 minutes, we will minimize the possibility of coercion or influence by providing subjects up to one hour to decide about participation and ample opportunity to reconsider their decision. They will have the opportunity to opt out at the interview or at any point on the study day, including while the study is underway.

The RA conducting the process will determine that the subject understands the information provided and is capable of making and communicating an informed consent. If they still wish to enroll they will complete the written informed consent document (contained in a separate document from this protocol).

Copies of the signed consent form and HIPAA document are retained by the participant and the Project Director. The date of signing will be considered their study enrollment date. This date will be recorded on the study participant's case report form. Forms will be kept in locked filing cabinets separate from all data. All individuals responsible for obtaining consent will have up to date CITI training.

After providing written consent participants will complete the baseline assessments described in Table 6.2.

After all baseline assessments are completed, participants will be randomly assigned to one of the two study arms. Randomization will be stratified by site and asthma severity (see table below) with each stratum in randomly allocated blocks of two using the ralloc program in Stata.^{82, 83} The RA will generate the random allocation sequence, will communicate randomization status to each participant at time of randomization and the allocation table will be uploaded to the RedCap database. Participants in each cohort will be randomized altogether and sent to the same MBSR and HLC classes. This approach is necessary to ensure that the seasonality and temporal differences be balanced between the two arms. We anticipate participants will begin their treatment program (MBSR or HLC) within 8 weeks of randomization.

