Retention of Participants: We expect to retain 85% of participants at 18-months. Contact information will be collected from the participant at enrollment. Tracking procedures will be established and implemented for those not completing a scheduled study assessment, or who cannot be reached. Attempts to locate participants will be made by telephone calls to family, family contacts, and directory assistance. Incentive gift certificates will be provided: \$50 for completing assessments at each of the baseline and 6-month follow-ups, and \$75 at 12- and 18-month follow-up. The UMMS Project Director, [name] will oversee retention at both sites.

6.2.3. Blinding: All study staff except the Research Assistant, and Project Director Database Manager ([name]) will be blinded. Blinding the Research Assistant, Project Director, and Database Manager would be impractical given that they will be randomizing the patients to the intervention groups, or tracking the randomization process. The impact of un-blinding the Research Assistant, the Project Director and the database manager will be minimal because evaluation surveys are completed directly by participants, and they will NOT perform any data entry or statistical analysis. The pulmonary lab technicians (for outcomes measurement) will be blinded, as well as the PIs, study statistician, and all study investigators and those involved with randomization codes. These un-blinded staff will have no access to the data, no influence on the outcome assessments, and no involvement in data analysis. Staff delivering the interventions and preparing reports for the independent monitoring will not be blinded.

The study arms will be coded and referred as non-informative A vs. B, but not intervention vs. control, or a coding revealing the nature of intervention arms. The non-informative coding/naming of intervention arms will be kept until the planned main outcomes analysis is completed. Unblinded project staff are prohibited to reveal the information on the coding of study arms to anyone.

The blind will be broken in the case of a serious adverse event. In this event, Drs. [name] and [name], the study pulmonary physicians, will break the blind in order to address the SAE.

The data and safety monitoring board (DSMB) will also be blinded unless the unblinding is needed to investigate severe adverse events or other patient safety issues, required by NCAAM, IRB or law.

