In case the unblinding is necessary, the process will be formally monitored and documented. The PI's will draft a request for permission to unblind the codes to NCCAM, IRB and the DSMB. With the permission, the PI's will work with the database manager to reveal the study arm codes to the individuals authorized by the PI's, DSMB, NCCAM and DSMB. Hand signed documents will be kept by the database manager, and copied to DSMB, IRB and NCCAM. Unblinded individuals will be excluded from first round of statistical analysis of the main outcomes.

6.2.4 Follow-up Visits: As described in Section 6.1, study follow-up visits will occur 6- months, 12- months, and 18-months post-baseline. Section 6.2 describes the assessments that will occur at each of these time-points. Study assessment visits indicated in Section 6.2 will occur within a 3-week period before and after the 6-, 12-, and 18-month timeframes.

6.2.5 Completion/Final Evaluation: The final evaluation will be conducted at the 18-month post-baseline assessment and will consist of the assessments listed in Section 6.2 for this visit. We do not foresee any reason for participants' early termination from the study. However, any participants who discontinue study intervention early will be invited to complete all study evaluations.

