the contact Principal Investigator. Contact information for the RA and the PI, as well as the IRB (for complaints) is provided in the consent form. Copies of the signed consent form are retained by the study and the participant. Participants are given ample opportunity to ask questions before providing consent. [name] the Project Director will supervise the RA to maintain consistent delivery of the orientation sessions. Study eligibility criteria include being aged 18 and over, and being able to read and understand English, and complete informed consent process and study data collection procedures.

After providing written consent they will complete the baseline assessments and be randomly assigned to one of the two study arms by the data manager at UMMS. Randomization will be stratified by site and asthma severity with each stratum in randomly allocated block sizes of two using the ralloc program in Stata.^{82, 83} The randomizations will be conducted for each cohort to ensure that the seasonality and temporal effects be adequately controlled by design.

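### The research assistant role that screens and consents patients is told to generate the allocation sequence, two other sections give randomization to the data manager, and nothing conceals upcoming assignments from enrolling staff

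*Combined protocol and SAP*

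**What the plan says.** **Generation and assignment by the RA.** Section 4.3 says: "The RA will generate the random allocation sequence, will communicate randomization status to each participant at time of randomization". Section 6.2.2 repeats it ("The RA will generate the random allocation sequence"). The severity paragraph of 6.2.2 adds that, once the two pulmonologists agree on the stratum, "the RA will then randomize the participant according to this classification". Both sections have the allocation table uploaded to REDCap and state no access limit for it.

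**The same role enrols.** Under 4.3 the RA at each site makes the screening call and completes the eligibility screen. Under 6.2.2, "The RA conducting the process will determine that the subject understands the information provided and is capable of making and communicating an informed consent". The attendance paragraph of 4.3 has the RA ask about planned absences; a patient expecting to miss more than one class is advised to join the next cycle.

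**Randomization by the data manager.** Section 3 says: "Randomization will be done by the data manager at UMMS". Section 11.2 says that participants will "be randomly assigned to one of the two study arms by the data manager at UMMS".

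**Codes.** Section 9.2 refers to 6.2.3 for how the randomization codes are maintained. Section 6.2.3 leaves the RA, Project Director and Database Manager unblinded, "given that they will be randomizing the patients to the intervention groups, or tracking the randomization process". It labels the arms A and B until the main analysis is done, forbids unblinded staff to reveal the coding, and, for a formal unblinding, provides that the PIs "will work with the database manager to reveal the study arm codes".

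**Timing.** Assignment follows written consent and all baseline assessments (4.3, 6.2.2). Each cohort is randomized as a group (Précis, 4.3, 6.2.2, 11.2).

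**The concern.** Allocation concealment means that whoever decides whether, and when, a patient enters cannot know the assignment that awaits. Sections 4.3 and 6.2.2, followed as written, give the sequence to the role that makes those decisions. If upcoming assignments are visible while a cohort is still filling, screening effort, consent discussions and deferral can depend on them, even without intent. The arms may then differ at baseline for reasons other than chance. The covariate adjustment in 9.6 can correct only the part of that difference that was measured.

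Section 6.2.3 argues that leaving these staff unblinded matters little because participants complete the surveys themselves and these staff do no data entry or analysis. That argument addresses bias in assessment and analysis. It does not address selection before assignment.

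**Working it through.** No sample size, power or alpha figure is involved, so the check is mainly a comparison of passages.

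**1. Can the role statements be reconciled?** One could suppose that the RA makes the list and the data manager applies it. That would fit 4.3 with Sections 3 and 11.2. It does not fit the severity paragraph of 6.2.2, where the RA randomizes. It would also leave the person who made the list knowing it. The reverse split (the data manager holds the list and the RA only triggers assignment) contradicts the generation sentence in 4.3 and 6.2.2. Section 6.2.3 does not settle the matter: it names three roles together as randomizing or tracking, and one of its sentences appears to count those who handle the codes among the blinded. Neither 4.3 nor 6.2.2 says which site's RA makes the list.

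**2. Does 6.2.3 conceal upcoming assignments?** It contains real rules on codes: neutral labels, a ban on disclosure, and release through the database manager. The ban controls what unblinded staff may tell others. Since the RA is one of the unblinded staff, it does not keep the list from the RA. Nothing there concerns assignments not yet made.

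**3. Does the timing conceal them?** The documents fix when patients are assigned: after baseline, by cohort. They do not fix when the list is made. A list drawn up after a cohort closes can influence no enrolment decision in that cohort. A list drawn up earlier can, if recruiting staff see it.

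**4. How many participants could be affected?** Inputs: 254 participants, 127 per site (9.2); 13 cohorts (Section 3).

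- Per site and cohort: 127 / 13 = 9.8.
- Both sites, per cohort: 254 / 13 = 19.5.
- Section 4.3 expects about 10 to 11 per cohort without saying whether this is per site. 13 × 10 = 130 and 13 × 11 = 143 are close to 127 and far from 254, so a per-site reading fits.
- List made after every cohort closes: 0 of 254.
- List made before closure and visible to recruiting RAs in every cohort: 13 × (254 / 13) = 254, the whole trial.

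The upper figure is a ceiling. It also supposes that a place on the list can be matched to a particular patient before the batch is run, which the documents do not describe.

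**The case against.** The strongest reply is that the harm needs a fact the documents do not state: a list made before the cohort closes and seen by recruiters. The safeguards are substantial. Assignment comes after consent and baseline. Each cohort is randomized together. Two pulmonologists determine severity, so the RA does not choose the stratum. Screening uses a script and a standard form under supervision. The Screening Form records reasons for ineligibility and non-participation, which leaves a trail for checking selective enrolment. Deferral starts from the patient's own planned absences. At UMMS, physicians strike unsuitable patients from the mailing list. All of this stands and narrows the RA's discretion, but none of it hides a list that already exists.

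A reader might infer three stronger things that the documents do not support:

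- **That enrolment was steered.** Nothing shows this. The text only leaves it possible.
- **That blocks of two make assignments predictable.** That would follow if patients were assigned one at a time. The plain reading is batch assignment of a cohort whose members have all completed baseline, so earlier assignments in the batch reveal nothing useful about patients still being recruited. Whether the list restarts with each cohort is not stated, and no figure for predictability is offered here.
- **That the plan has no rules for the codes.** Section 6.2.3 has several. The gap is narrower: concealment before assignment.

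It is also fair to say that the data manager may hold the list in practice, as the unblinding procedure suggests. The generation sentence in 4.3 and 6.2.2 still says otherwise.

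**Conclusion.** The point holds as a contradiction about who randomizes, combined with a gap in concealment. Sections 4.3 and 6.2.2 place generation and assignment with the enrolling role, Sections 3 and 11.2 place randomization with the data manager, and no available section keeps upcoming assignments from enrolling staff or dates the list. Exposure runs from 0 to 254 participants, depending on two facts that the documents omit: when each list is made and who can see it. The contradiction is certain from the text. The bias is conditional, and its effect on the ACQ cannot be estimated from the documents. This should be fixed; it is not evidence that the comparison is compromised. The conclusion rests on the text available, from which some pages were removed.

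**What to change.** In 4.3 and 6.2.2, replace the sentence that has the RA generate the sequence with wording such as:

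> *The data manager at UMMS, who takes no part in screening, consent or enrolment, generates the allocation sequence and makes the assignments. Recruiting staff cannot view the REDCap allocation table. Assignments for a cohort are released only after consent, eligibility, baseline, severity class and any deferral are locked for all its members.*

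The RA may still tell participants their assignment. Bring Sections 3, 6.2.2 (including the severity paragraph), 6.2.3 and 11.2 into line, and state when the list is made and whether it restarts with each cohort.

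Two conditions need checking. First, the documents do not establish that the data manager is free of enrolment duties. Section 6.2.3 at one point runs the Project Director and Database Manager titles together, and the Project Director oversees recruitment (4.3). Second, the plan should say whether the data manager (Sections 3 and 11.2), the Database Manager (6.2.3) and the study data manager (10.3.3) are one role. If they are, the holder of the allocation table also audits all outcome points each month. The arm field should then be hidden in that audit, which limits that exposure but does not remove it.

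The cost is wording in Sections 3, 4.3, 6.2.2, 6.2.3, 10.3.3 and 11.2 and a REDCap permission. No new staff are needed if the data manager meets the first condition; otherwise someone independent of enrolment must be named. If recruitment has closed, the sponsor should document who generated each list, when, and who could see it.
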